5.2.2. Phase 1: Baseline Procedures for Baseline Visits 1 (93) and 2 (92)

During Phase 1 of baseline (screening up to access to tobacco marketplace), eligible subjects will continue to smoke their preferred brand as usual. At the baseline clinic visits, subjects will complete several measures and provide biomarker samples as described below.

A. *Physiological Measures at Baseline (93 and 92):*

- 1) BrAC, which must be below 0.03 g/210L. If over the 0.03, the visit will be delayed until the level drops within range or subject can be rescheduled. If above 0.05, the visit will be rescheduled. Multiple baseline elevated BrAC results may result in discontinuation of the subject at the PI discretion. (BrAC was discontinued in conversion to telehealth visits.)
- 2) Expired breath CO level.
- 3) Vitals signs (blood pressure, heart rate).
- 4) Weight.
- 5) First morning void urine collected.
- 6) Saliva samples:
 - a) Saliva sample obtained with Salivette (with citric acid preparation) to be used for nicotine metabolite ratio (NMR) Visit 1 (93) only.
- 7) Spot urine for pregnancy tests [hCG detection] will be performed for female participants of childbearing potential (not surgically sterilized or 2 years post-menopausal) at Week

92 prior to offering Marketplace. (Pregnancy tests are performed on first morning void after conversion to telehealth visits.)

B. Questionnaires and Assessments at Baseline (93 and 92):

B.1 Web-based data collection program completed by the subject:

- 1) Minnesota Nicotine Withdrawal Scale (MNWS).
- 2) Questionnaire of Smoking Urges- Brief - Usual Brand Cigarette (QSU).
- 3) Cigarette Evaluation Scale – Baseline (CES – Usual Brand).
- 4) Respiratory and Global Health Questionnaire.
- 5) If monitored for psychiatric illness: Beck Depression Inventory 2nd Edition (BD-II) (paper only).
- 6) Cigarette Dependence Measures (Usual Brand - Visit 93 only).
- 7) Environmental Tobacco Smoke Exposure Questionnaire (Visit 93 only).
- 8) Social and Environmental Influences on Tobacco Use (Visit 93 only).
- 9) Dietary Intake (e.g., charred and smoked meats and fish) (Visit 93 only).
- 10) NIAAA Alcohol Use Questionnaire - 1 month version (Visit 93 only).
- 11) Expected Utility (ANDS) (Visit 93 only).
- 12) Perceived Health Risk of no tobacco use, usual brand cigarettes, very low nicotine cigarettes, smokeless tobacco/snus/nicotine pouches, medicinal nicotine, ENDS (Visit 92 only).
- 13) Product Expectancy Questionnaire (Visit 92 only).

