5.2.4. Phase 2: Marketplace Adaptation Visit (00) Procedures

A. Physiological Measures at MP 00:

- 1) BrAC (discontinued at telehealth visits).
- 2) Expired breath CO level.
- 3) Vitals signs (blood pressure, heart rate).
- 4) Weight.
- 5) First morning void urine.
- 6) Spot urine for pregnancy tests [hCG detection] will be performed for female participants of childbearing potential (not surgically sterilized or 2 years post-menopausal) at Week 00. (Pregnancy tests are performed on first morning void after conversion to telehealth visits.)

B. Questionnaires and Assessments at MP 00:

B.1 Web-based data collection program completed by the subject:

- 1) Minnesota Nicotine Withdrawal Scale (MNWS).
- 2) Questionnaire of Smoking Urges-Brief -Usual Cigarette (QSU).
- 3) Cigarette & Product Evaluation Scale – (Baseline Usual Brand CES/PES).
- 4) Respiratory and Global Health Questionnaire.
- 5) CES-D:
Beck Depression Inventory 2nd Edition (BD-II) will be administered on paper if the CES-D score is 16 or greater or if monitored for psychiatric illness.
- 6) Cigarette Dependence Measures (Usual brand)
- 7) Environmental Tobacco Smoke Exposure Questionnaire
- 8) Dietary Intake.
- 9) NIAAA Alcohol Use Questionnaire (1 month).
- 10) Perceived Health Risk of no tobacco use, usual brand cigarettes, very low nicotine cigarettes, smokeless tobacco, medicinal nicotine and ENDS.
- 11) Contemplation Ladder.
- 12) Cigarette (Usual Brand and All Products) Purchase Task.

B.2 Administered as an interview by the study Research Assistant (entered into REDCap):

- 1) Health Changes Questionnaire.
- 2) Adverse Events.
- 3) Concomitant Medications.
- 4) Review of Daily Call and follow-up of missing and unusual reports.
- 5) Timeline Followback Questionnaire.
- 6) Recreational Drug Use Questionnaire (1 month version).
- 7) Product Accountability: Complete Product Dispensing Log.
- 8) Study Product and Procedures Compliance Review.
- 9) End of Visit Questionnaire.

Randomization and Marketplace with study cigarettes

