At the end of Visit 00, subjects will be randomized to one of the two experimental conditions (VLNC vs. NNC cigarettes) for 12 weeks. Twelve weeks was chosen because experimentation with or use of other tobacco/nicotine products is most likely to occur during the first weeks of intervention and stabilization is likely to occur thereafter. However, the time course of stabilization of product use is not clearly known, a 12 week duration of intervention was selected to allow sufficient time to observe any smoking cessation behaviors.

Subjects will be informed of the general nicotine content of the Spectrum cigarettes. Subjects assigned to the VLNC Spectrum cigarette condition will be informed they contain minimal amounts of nicotine to reduce their addictiveness and those assigned to the NNC Spectrum cigarettes will be informed that they contain levels of nicotine that are similar to the

conventional cigarettes that are currently on the market. Research cigarettes are provided under non-blind conditions because if a reduced-nicotine policy were to be implemented, the FDA would by necessity provide information to the public on the reduced nicotine content of cigarettes.

PHASE 3: INTERVENTION: STUDY CIGARETTES IN EXPERIMENTAL MARKETPLACE

Scheduling window at baseline is 7 days -3/+ 4 days and 14 days -6/+ 7 days for bi-weekly visits.

During the Phase 3 visits (Weeks 1-12), subjects will continue to acquire the study cigarettes and alternative nicotine products via the Marketplace website (no access to usual brand cigarettes). At the clinic visits, subjects will complete several measures and provide biomarker samples as described below.

5.2.5. Procedures for Phase 3 - Weeks 1, 2, and 3 (Week 3 was discontinued following telehealth procedure changes)

At these visits, the procedures will only involve access to products and checking records of product use and safety checks.

A. Physiological Measures at Weeks 1, 2 and 3:

- 1) BrAC (discontinued at telehealth visits).
- 2) Expired breath CO level.
- 3) Vitals signs (blood pressure, heart rate).
- 4) Weight.
- 5) Spot urine sample for compliance testing. (Saliva samples for compliance testing are collected at telehealth visits.)

B. Questionnaires and Assessments at Weeks 1, 2, and 3:

B.1 Web-based data collection program completed by the subject:

- 1) Minnesota Nicotine Withdrawal Scale (MNWS).
- 2) Questionnaire of Smoking Urges-Brief - Study Cigarette (QSU).

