- 3) Cigarette & Product Evaluation Scale – (Study Cigarettes CES/PES).
- 4) Respiratory and Global Health Questionnaire.
- 5) If monitored for psychiatric illness: Beck Depression Inventory 2nd Edition (BD-II) (paper only).

B.2 Administered as an interview by the study Research Assistant (entered into REDCap):

- 1) Health Changes Questionnaire.
- 2) Adverse Events.

- 3) Concomitant Medications.
- 4) Review of Daily Call and follow-up on missing and unusual reports.
- 5) Timeline Followback Questionnaire (since last visit).
- 6) Study Product Accountability: Complete product dispensing log.
- 7) Study Product and Procedures Compliance Review.
- 8) End of Visit Questionnaire.

5.2.6. Procedures for Phase 3 - Weeks 4, 8 and 12

A. Physiological Measures at Weeks 4, 8 and 12:

- 1) BrAC (discontinued at telehealth visits).
- 2) CO level.
- 3) Vitals signs (blood pressure, heart rate).
- 4) Weight.
- 5) First morning void urine sample.
- 6) Spot urine for pregnancy tests [hCG detection] will be performed for female participants of childbearing potential. (Pregnancy tests are performed on first morning void after conversion to telehealth visits.)
- 7) Spot urine sample for compliance testing. (Saliva samples for compliance testing are collected at telehealth visits.)
- 8) Drug screen (Week 12 only). (Discontinued at telehealth visits.)

B. Questionnaires and Assessments at Weeks 4, 8 and 12:

B.1 Web-based data collection program completed by the subject:

- 1) Minnesota Nicotine Withdrawal Scale (MNWS).
- 2) Questionnaire of Smoking Urges-Brief-Study Cigarette (QSU).
- 3) Cigarette & Product Evaluation Scale – (Study Cigarettes CES/PES).
- 4) Respiratory and Global Health Questionnaire.
- 5) CES-D:
Beck Depression Inventory 2nd Edition (BD-II) will be administered on paper if the CES-D score is 16 or greater or if monitored for psychiatric illness.
- 6) Cigarette Dependence Measures (Study Cigarettes).
- 7) Environmental Tobacco Smoke Exposure Questionnaire.
- 8) Dietary Intake.
- 9) NIAAA Alcohol Use Questionnaire (1 month).
- 10) Social and Environmental Influences on Tobacco Use (Week 12 only).

- 11) Perceived Health Risk of no tobacco use, usual brand cigarettes, study cigarettes, smokeless tobacco, medicinal nicotine and ENDS (Week 12 only).
- 12) Cigarette/Product Purchase Task (Week 12 only).
- 13) Vaping/Product Dependence Scale (week 12 only)

B.2 Administered as an interview by the Research Assistant (entered into REDCap):

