5.7.5. Subjective Outcome Measures

- 1) *Interactive Voice Response – Daily Call Recording System* to record amount of product use, cigarettes, and other nicotine containing products on a daily basis (estimated ENDS puffs per day will be recorded),.
- 2) *Timeline followback* for tobacco³⁵ will be used as another measure of non-cigarette tobacco and nicotine intake), alcohol and marijuana use assessed at each clinic visit.
- 3) *IVR Review Form* will assess study and non-study use of cigarette and other products missing from the IVR calls, correct errors in IVR entries or clarify any discrepancies or unusual IVR reports.
- 4) *Cigarette/Vaping Dependence Measures* includes: Fagerstrom Test for Nicotine Dependence (FTND),³⁶ Penn State Cigarette Dependence Scale,³⁷ Brief Wisconsin Inventory of Smoking Motives (WISDM) primary dependence motives subscales³⁸ and 3 items from PATH.
- 5) *Severson Smokeless Tobacco (SLT) Dependence Questionnaire* is an 8 item measure to assess tobacco dependence.³⁹
- 6) *Minnesota Nicotine Withdrawal Scale (MNWS)* is an 8 item assessing symptoms of tobacco withdrawal.⁴⁰
- 7) *Questionnaire of Smoking Urges-Brief* 10 item measures the urge to smoke.⁴¹
- 8) *Adverse Events* to assess the nature, severity, duration, action taken, and outcome of adverse events related to tobacco/nicotine product use.
- 9) *Health Changes Questionnaire* queries for any health care visits or circumstances that would indicate any change since last visits.
- 10) *Respiratory and Global Health Questionnaire* rates overall health (1-10 scale) and respiratory symptoms such as cough, phlegm production, shortness of breath on a scale

ranging from 0 = none up to 10 = severe with a total respiratory score determined by adding the scores of each of these items.

- 11) *NIAAA Alcohol Use Questionnaire (1 and 12 month)* assesses frequency and quantity of alcohol use.⁴²
- 12) *Recreational Drug Use History (1 and 12 month)* assesses amount, frequency in past year, and past month and date of last use of illicit drugs.
- 13) *Perceived Health Risks* assesses perceived health risks of no tobacco use, usual brand of cigarettes and study products that are provided.⁴³
- 14) *Modified Cigarette Evaluation Scale⁴⁴⁻⁴⁶ and/or Product Evaluation Scale⁴⁷* assesses different dimensions of responses to cigarettes or other tobacco/nicotine products, (e.g., psychological reward, satisfaction, aversiveness, and additional oral and respiratory sensation items).

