5.3. Exploratory Endpoint

- Non-combusted tobacco/nicotine products use: the number of days using any non-combusted tobacco/nicotine products in Phase 3.
- Characteristics' of products chosen (type, flavor, nicotine strength).
- Biomarkers: percent change in biomarkers (Total Nicotine Equivalents, total NNAL, mercapturic acids at the weeks 4, 8 and 12 visits during Phase 3 as compared to the last visit in Phase 2).
- Product satisfaction (Product Evaluation Scale if they used the product since the last visit; Cigarette Evaluation Scale if they smoked cigarettes since the last visit).
- Perceived health risk (Phase 1, Phase 2 and end of week 12 of Phase 3: all products for all subjects).
- Measures of discomfort/dysfunction: MNWS-R, QSU, CESD (NNC vs VLNC cigarettes irrespective of use of products).
- Dependence (FTND, WISDM, PATH items; monthly for study cigarettes).

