6.3.2. Secondary Analysis

For the Week 12 CPD and total number of smoke-free days, we will perform an adjusted analysis, adjusting for baseline value, study site (the randomization stratification factor), whether the Week 12 visit is pre-COVID or not, and any baseline characteristics (listed in Section 6.2) which are different at $p<0.20$, in multivariable regressions to improve efficiency.

For the CPD outcome measured repeatedly, we will use linear mixed effects models (Verbeke and Molenberghs, 2000). Fixed effects in the model will include: treatment group, visit, treatment group by visit interaction, baseline CPD, study site, whether the visit time is pre-COVID or not (as a time-dependent covariate), and any baseline characteristics (listed in Section 6.2) which are different at $p<0.20$. A random intercept for each subject will also be included in the model to account for within subject correlation.

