6.5. Exploratory Endpoint Analysis

- For the number of days of non-combusted tobacco/nicotine products use, we will use Poisson or negative binomial regression, adjusting for baseline value, study site, whether the visit is pre-COVID or not, and any baseline characteristics which are different at $p < 0.20$.
- We will descriptively examine the characteristics of the various products that are chosen (type, nicotine strength, flavor).
- For other biomarkers, similar analyses to Secondary Endpoint will be performed.
- Product satisfaction (Product Evaluation Scale, Cigarette Evaluation Scale) at the first time a participant tried a product will be summarized using mean and standard deviation and compared between two treatment arms using linear regression.
- Repeated measures of perceived health risk will be analyzed using the mixed effects model as described in Section 6.3.2.
- Discomfort as assessed by MNWS-R, QSU, CESD will be compared between the VLNC vs. NNC cigarette conditions. The methods for comparing discomfort measures between VLNC and NNC cigarettes will be the same as for those described for the primary endpoints in Section 6.3.
- Repeated measures of dependence of study cigarettes will be analyzed using mixed effects model described in Section 6.3.2.
- We will examine the cross-sectional associations of non-combusted products use with cigarettes smoked and biomarkers at different visits using marginal generalized estimating equations (GEE) model (Diggle et al, 2002, Chapter 12) with the non-combusted product use as the independent variable.
- We will explore baseline predictors of responses. We will use multivariable regressions to determine predictors of product use patterns, e.g., non-combusted product use, combusted product use, and smoke-free days. Predictor variables (depending on the responses measured) will include baseline CPD, total nicotine equivalents, FTND, age, sex, racial ethnic group, SES, perceived risk of products, product expectancy, product utility, social and environmental influences, contemplation ladder, menthol cigarette use, and nicotine metabolite ratio (NMR, reflecting rate of nicotine metabolism). Similar regression models as described in Sections 6.3 and 6.4 will be used.

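### Perceived VLNC risk has no listed Week 12 rating in the NNC arm, and the planned mixed model leaves the other items' Week 12 comparison unadjusted for their own baseline rating

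*Combined protocol and SAP*

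**What the plan says.** SAP 5.3 lists the exploratory endpoint as "Perceived health risk (Phase 1, Phase 2 and end of week 12 of Phase 3: all products for all subjects". SAP 6.5 gives the analysis: "Repeated measures of perceived health risk will be analyzed using the mixed effects model as described in Section 6.3.2". Protocol 16.6.5 does the same by reference to its Secondary Analysis section. The model in SAP 6.3.2 was written for repeated CPD: "Fixed effects in the model will include: treatment group, visit, treatment group by visit interaction, baseline CPD, study site", then a COVID-period term, any imbalanced baseline characteristics and a random intercept per subject. It names baseline CPD but no baseline risk rating.

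The ratings are scheduled as follows.

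- Visit 92, Phase 1 (protocol 5.2.2): "Perceived Health Risk of no tobacco use, usual brand cigarettes, very low nicotine cigarettes, smokeless tobacco/snus/nicotine pouches, medicinal nicotine, ENDS (Visit 92 only".
- Visit 00, Phase 2 (protocol 5.2.4): "Perceived Health Risk of no tobacco use, usual brand cigarettes, very low nicotine cigarettes, smokeless tobacco, medicinal nicotine and ENDS".
- Week 12, Phase 3 (protocol 5.2.6): "Perceived Health Risk of no tobacco use, usual brand cigarettes, study cigarettes, smokeless tobacco, medicinal nicotine and ENDS (Week 12 only".

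The early termination list in protocol 13.4 also has study cigarettes and no very low nicotine item. Protocol 5.7.5 says the instrument "assesses perceived health risks of no tobacco use, usual brand of cigarettes and study products that are provided". On timing, protocol 5.2.4 says: "At the end of Visit 00, subjects will be randomized to one of the two experimental conditions".

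**The concern.** Two features of the schedule sit badly with a repeated-measures comparison of arms.

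First, the cigarette item changes. Before randomisation everyone rates very low nicotine cigarettes. Afterwards each participant rates the assigned study cigarette, which is a different product in each arm. A Week 12 difference on that item could be misread as an effect of assignment on how risky VLNC cigarettes seem, when it compares ratings of two products. Protocol 2.3 notes that knowing the nicotine content may influence beliefs about the cigarettes, so the misreading would touch a question of policy interest.

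Second, two of the three ratings precede treatment. The SAP does not say which ratings are outcomes, which are baseline, or which term is the treatment effect. The model it borrows adjusts for baseline CPD and not for the earlier rating of the same item.

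**Working it through.** The documents give no power, SD or effect size for this endpoint, so there is no stated figure to reproduce.

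**Ratings available, by item and arm**

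| Item | Visit 92 | Visit 00 | Week 12, VLNC arm | Week 12, NNC arm |
|---|---|---|---|---|
| No tobacco use, usual brand, smokeless tobacco, medicinal nicotine, ENDS | both arms | both arms | yes | yes |
| VLNC cigarettes | both arms | both arms | yes, as study cigarettes | none listed |
| NNC study cigarettes | none | none | none | yes |

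**What the model can estimate.** The arm and visit part of SAP 6.3.2 has 1 (intercept) + 1 (arm) + 2 (visit) + 2 (arm by visit) = 6 columns. Each arm-by-visit cell with data supplies one independent row.

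- Five items rated throughout: 2 × 3 = 6 cells, rank 6 of 6. The model can be fitted, and the arm difference at Week 12 is estimable.
- VLNC item: 6 − 1 = 5 cells, rank 5 of 6. The Week 12 arm difference is not estimable.
- NNC study cigarettes: 1 cell, rank 1 of 6. There is no earlier rating to compare with.

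**Precision for the five items.** Assumptions:

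- 160 per arm, from 200 per group and 20% attrition in SAP 3.2: 200 × 0.80 = 160.
- Rating SD of 1, so results are in SD units.
- Correlation r between the Visit 00 and Week 12 ratings, which the documents do not give.

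Unadjusted Week 12 difference: SE = √(2/160) = 0.112. Adjusting for the Visit 00 rating multiplies this by about √(1 − r²):

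| r (assumed) | √(1 − r²) | Adjusted SE |
|---|---|---|
| 0.3 | 0.954 | 0.107 |
| 0.5 | 0.866 | 0.097 |
| 0.7 | 0.714 | 0.080 |

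A simulation of 200 runs used the same assumptions, with r = 0.5, a true Week 12 effect of −1 and no earlier difference:

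| Estimate | Mean | SD over runs |
|---|---|---|
| Week 12 arm contrast from the three-visit mixed model | −0.98 | 0.113 |
| Regression of Week 12 rating on arm and Visit 00 rating | −0.99 | 0.094 |
| Arm effect averaged over the three visits | −0.32 | 0.088 |

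The first two recover the true effect, and the regression is more precise. The third is diluted as arithmetic predicts: with expected arm differences of 0, 0 and d, the mean is (0 + 0 + d)/3 = d/3.

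**If the earlier ratings were instead used only as baseline.** One outcome row per person remains. Two cells give rank 2 of 6, the visit and interaction terms drop out, and the random-intercept variance cannot be separated from the residual.

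**The case against.** A reader might infer that the planned model cannot be fitted at all, because only one rating follows randomisation. The documents do not support that. SAP 5.3 names three time points, SAP 6.5 calls them repeated measures, and SAP 6.3.2 does not move a risk rating into the covariates. The natural reading is three outcome rows per person. For the five items rated throughout, that is an estimable model with a valid Week 12 contrast. The single-row failure arises only under a reading that the SAP does not state.

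A reader might also infer that the treatment effect will be diluted to one third. That happens only if an arm effect averaged over visits is reported, and the SAP does not say it will be. The interaction term isolates Week 12.

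Three further points have weight.

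- The words about all products and all subjects probably mean regardless of use, since the satisfaction endpoint just above them is limited to products used. The Week 12 list also agrees with protocol 5.7.5. This explains the wording but does not supply a Week 12 VLNC rating in the NNC arm.
- The questionnaire itself is not in the documents and the visit lists are summaries: Visit 92 names snus and nicotine pouches with smokeless tobacco, and Visit 00 does not. The gap is therefore in the listed items. The early termination list has the same gap.
- No stated aim has a hypothesis about perceived VLNC risk. Change in VLNC rating within the VLNC arm, and each arm's rating of its own assigned cigarette, remain available.

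**Conclusion.** The concern holds in a limited form. From the listed items, a between-arm comparison of perceived VLNC risk at Week 12 is not estimable, and NNC study cigarettes have no earlier rating. For the five items listed at all three visits, the planned model works and its Week 12 contrast is valid. Its weaknesses are an unnamed treatment contrast and no adjustment for the item's own baseline rating.

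The size of the second weakness is a loss of precision, not bias: a standard error of 0.112 where about 0.097 was attainable, assuming r = 0.5, SD 1 and 160 per arm. Over r from 0.3 to 0.7 the attainable value runs from 0.107 to 0.080. The first conclusion rests on the visit lists matching the questionnaire actually used. Severity is minor: the endpoint is exploratory, and the primary and secondary conclusions do not depend on it.

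**What to change.** In SAP 6.5 and protocol 16.6.5:

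1. Name the items to be analysed: those rated at both Visit 00 and Week 12.
2. For each, regress the Week 12 rating on arm and the Visit 00 rating of the same item, and state that the arm coefficient is the treatment effect. No random intercept is needed.
3. Report the study cigarette rating descriptively by arm, and state that it is not a between-arm effect on perceived VLNC risk.

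This uses data already collected and costs a few lines of SAP and protocol text.

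Adding the very low nicotine item at Week 12 in both arms would help only participants who have not yet reached that visit. The synopsis gives enrolment to 9/30/2022, and the SAP was last modified on 11/21/2022. By the durations in protocol section 8, someone screened on the last enrolment day would reach Week 12 about 1 + 2 + 2 + 12 = 17 weeks later, in late January 2023. The item could therefore reach only the latest participants and would not restore the comparison for the trial as a whole.
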